5.2 Exclusion Criteria

1. Currently pregnant or successful pregnancies within 12 months of initiating participation. Clinical intrauterine miscarriages prior to initiating participation, within ASRM guidelines: subjects 35 and over must wait six months, while subjects under 35 must wait 12 months. No exclusion for biochemical pregnancies.
2. Undiagnosed abnormal uterine bleeding.
3. Suspicious ovarian mass.
4. Subjects on oral contraceptives, depo-progestins, or hormonal implants (including Implanon). A two month washout period will be required prior to screening for patients on these agents. Longer washouts may be necessary for certain depot contraceptive forms or implants, especially when the implants are still in place. A one-month washout will be required for patients who have taken oral cyclic progestins.
5. Known 21-hydroxylase deficiency or other enzyme defect causing congenital adrenal hyperplasia.
6. Type I or Type II diabetes mellitus, or if receiving antidiabetic medications.
7. Known significant anemia (Hemoglobin <10 g/dL).
8. History of deep venous thrombosis, pulmonary embolus, or cerebrovascular event.
9. Known heart disease (New York Heart Association Class II or higher).

10. Known liver disease (defined as AST or ALT >2 times normal, or total bilirubin >2.5 mg/dL).
11. Known renal disease (defined as BUN >30 mg/dL or serum creatinine > 1.4 mg/dL).
12. History of, or suspected cervical carcinoma, endometrial carcinoma or breast carcinoma.
13. History of alcohol abuse (defined as >15 drinks/week) or binge drinking of ≥ 6 drinks at one time).
14. Known Cushing's disease.
15. Known or suspected adrenal or ovarian androgen secreting tumors.
16. Allergy, known hypersensitivity or contraindication to the treatment medications used in this study including orlistat (This will include patients with chronic malabsorption syndrome or cholestasis or clomiphene (previous change in vision).
17. Couples with previous sterilization procedures (e.g. vasectomy, tubal ligation) whether or not it has been reversed.
18. Subjects with untreated poorly controlled hypertension defined as a systolic blood pressure ≥ 160 mm Hg or a diastolic ≥ 100 mm Hg obtained on two measures obtained at least 60 minutes apart.
19. Subjects who have undergone a bariatric surgery procedure in the past or are in a period of acute weight loss (defined as a weight loss of greater than 5% body weight in the last 6 months).
20. Known severe endometriosis

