6.1.1 Determine Baseline Physical Activity

Subjects will be dispensed a Fitbit Physical Activity monitor during the randomization visit which will be used to determine average daily steps over a week's time.

Standard Physical Activity Intervention: This will be identical to the physical activity described above for the intensive physical activity group. There will be no dietary recommendations, no use of meal replacements, and no use of anti-obesity drugs. Subjects will have the same monitoring schedule both on site and off site as subjects in the intensive lifestyle modification.

Conception during Lifestyle Modification We will encourage intercourse without barriers during the lifestyle modification phase and welcome any pregnancies which happen. They will be managed identically as though that occur during the empiric infertility treatment phase of this study (Phase II below). Of course such pregnancies will be analyzed by treatment group according to intention-to-treat (ITT) principles. We are using safe and widely utilized lifestyle modifications. We are using an OTC weight loss drug, Alli, that has no known early adverse pregnancy effects and we will immediately discontinue it if pregnancy occurs. The ability to conceive at all points in this study will increase the appeal to participate and also the external validity of our results. No one with infertility wants to stop attempting pregnancy as part of infertility treatment. This also led us to reject using the oral contraceptive pill as a control arm for unexplained infertility.

Phase II – Standardized infertility treatment

After completion of Phase I (or 16 weeks of pretreatment), all subjects will enter Phase II. This phase will be universally administered to all participants in an open label, but standardized fashion. In this part of the study, subjects will receive three cycles of ovarian stimulation/hCG

trigger for ovulation/ timed IUI and followed by midluteal visit. We will clamp weight and activity in both groups and continue to monitor with the Fitbit and the Aria scale. We will modify and streamline the study procedures from our AMIGOS study.

Phase III – Pregnancy

There will be no treatment intervention during pregnancy, though we will continue to monitor weight and have trimester study visits.

Phase IV – Pregnancy Registry

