Sonohysterogram or hysterosalpingogram to verify patency in at least one tube, and normal uterine cavity (or documentation within past 3 years). An uncomplicated intrauterine non-IVF pregnancy and uncomplicated delivery and postpartum course resulting in live birth within the last three years will also serve as sufficient evidence of a patent tube and normal uterine cavity as long as the subject did not have, during the pregnancy or subsequently, risk factors for Asherman’s syndrome or tubal disease or other disorder leading to an increased suspicion for intrauterine abnormality or tubal occlusion.

6. Laboratory tests.

Females:

- Collect blood for the following tests for inclusion/exclusion (Table 8) (if not already obtained)
- Offer optional blood test for Rubella, Varicella, and HIV. The costs for these blood tests are not included in determining the patient care budget for this protocol.
- Offer optional recommended genetic tests and hemoglobin electrophoresis per ACOG guidelines. The costs for these blood tests are not included in determining the patient care budget for this protocol.
- Collect central core blood specimen to be sent to a central laboratory for testing
- At each blood draw during the study, retain a reserve blood and urine specimen (aliquotted to at least 3 cc each) for banking on site for future ancillary studies as plasma and serum, if subject has consented for optional blood and urine collection.
- Collect vaginal microbiome swab and rectal microbiome swab.

Table 8: Female Local Laboratory Screening Blood Tests

FEMALE LOCAL LABORATORY SCREENING BLOOD TESTS	
Eligibility Labs (within 1 year)	Safety Screen (fasting) Labs
AMH*	Urine pregnancy test
Prolactin	Hemoglobin
TSH	Hematocrit
HgbA1c	WBC
	Platelets
	BUN
	Creatinine
	Total Bilirubin
	ALT/AST
	Total Cholesterol
	HDL-C
	Triglycerides

- In lieu of AMH to determine ovarian reserve to meet inclusion criteria, investigators can obtain or use a prior Day 3 (+/-2 day) FSH and Estradiol
- Eligibility tests in Column 1 are valid for one year prior to randomization.
- Safety Screen tests, except the lipid panel must be obtained within 60 days prior to randomization.
- Lipid Panel (cholesterol, triglycerides, HDL) results are valid for one year prior to randomization.

Males: obtain a semen specimen.

- Local lab semen analysis (or documentation within 1 year)
- Retain semen sample for future microarray analysis if RMN Biologic Repository consent is signed

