- Collect urine and blood sample for RMN Biologic Repository if consent is signed
- Collect saliva sample if consented

7. Distribute Testing and Study Supplies
 - a. Distribute salivary collection kit, if consented.

Randomization Visit:

Randomization visit can take place regardless of menstrual cycle day and as soon after screening visit as subject and couple meet inclusion/exclusion criteria. Subjects will be informed in person of their randomization assignment. This is to allow for in person counseling of the lifestyle modification and answer face to face any concerns about their treatment assignment. Subjects will undergo during this visit: extensive orientation to the goals of the lifestyle modification, dispensing of all supplies and medications, and review of tracking and self-reporting requirements.

1. Perform limited physical exam, including weight and vital signs.
2. Orient subject to study treatment group including activity recommendations and use of meal replacements and orlistat.
3. Dispense study supplies such as Aria Wifi scale and Fitbit Activity tracker.
4. Dispense weight loss medication (orlistat) and provide instructions for ordering meal replacements on Nutrisystem’s website to subjects randomized to the extensive lifestyle modification arm.
5. Dispense intercourse and menstrual diaries.
6. Prenatal vitamins with folic acid dispensed.
7. Collect central core blood specimen as well as urine and blood reserve sample for ancillary studies (to be stored on site) (with consent). This will include hormonal assays for sex steroids (E2, P4, Testosterone), other reproductive hormones (SHBG), adipokines (leptin, adiponectin) and other hormonal and metabolic parameters that are determined relevant to the study.

8. Collect blood for DNA for the pharmacogenomic studies (with consent) to be stored on site.
9. Collect all available biospecimens from subject and male partner for RMN Biologic Repository (with consent).
10. Collect saliva specimen (with consent).

Monthly Visit during Lifestyle Modification Phase (Phase 1) (N = 3)

1. Perform limited physical exam, including weight, waist circumference, and vital signs (respiratory rate, pulse, and blood pressure).
2. Perform urine pregnancy test.
3. Collect menstrual and intercourse diaries, dispense new for next month.
4. Collect remaining study medications and perform pill count.
5. Dispense study supplies and medications, Prenatal vitamin, if applicable, orlistat.

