10.4 Sample Size and Accruals

10.4.1 Sample Size and Power Calculations

Estimates used for the power calculation are based on our experience from the OWL PCOS and AMIGOS trials as provided in the preliminary data section. The primary outcome for this trial is a good birth outcome defined as an infant (singleton or twin) born at ≥ 37 weeks between 2500 and 4000g without a major congenital anomaly. We will examine the cumulative rates between groups. We anticipate the proportion of good birth outcomes to be 0.25 in the standard lifestyle intervention (physical activity and weight maintenance) arm and 0.40 in the Intensive lifestyle modification arm. We anticipate that there will be an increased proportion of good birth outcomes in each group beyond our preliminary data, as we will not actively prevent pregnancy during the lifestyle intervention; therefore, they will have an additional 16 weeks to conceive prior to initiating empiric treatment. A sample size of 190 per treatment arm will provide 80% power to detect a 0.15 absolute difference in the proportion of good perinatal births (0.25 in the standard lifestyle modification and 0.40 in the intensive group using a two-sided test having a significance level of 0.05. Although the randomization is stratified by two factors (recruitment site and BMI status), this factor was not taken into consideration for the power analysis to be conservative because accounting for the correlation of these covariates with the outcome would simply increase the precision, and hence, increase the power. The sample size has been inflated to a total of 380 participants to allow for a dropout rate of 20%. We believe this 20% dropout rate is a reasonable estimate based on current experience in our PPCOS I, PPCOS II, OWL PCOS, and AMIGOS trials. The table below summarizes other possible sample size scenarios having a 0.15 absolute difference in the proportion of good birth outcomes between the two treatment arms, all of which we would have excellent power to detect (**Table 11**).

Table 11: Sample size scenarios based on varying assumptions

Standard Lifestyle Modification: Physical Activity Arm having a Good Birth Outcome	Intensive Lifestyle Modification Weight Loss and Physical Activity Arm: Proportion having a Good Birth Outcome		Significance Level (alpha)	Power (%)	N per Arm (0% Dropout)	N per Arm (20% Dropout)
0.15	0.30		0.05	80	121	152
			0.05	90	161	202
0.20	0.35		0.05	80	138	173
			0.05	90	185	232

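### The pregnancy exclusion is not checked at randomization: the only required test may be 60 days old, so unrecognised early pregnancies can be randomized and their births counted in the primary outcome

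*Combined protocol and SAP*

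**What the plan says.** Section 5.2, item 1 excludes women who are "Currently pregnant or successful pregnancies within 12 months of initiating participation". Section 5.6 requires both partners to be confirmed against all criteria before randomization.

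The test behind that confirmation is the urine pregnancy test in the Safety Screen column of Table 8 (Section 7.2). Its timing rule is "Safety Screen tests, except the lipid panel must be obtained within 60 days prior to randomization".

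For the randomization visit, Section 7.2 says "Randomization visit can take place regardless of menstrual cycle day and as soon after screening visit as subject and couple meet inclusion/exclusion criteria". None of the ten procedures listed for that visit is a pregnancy test. Table 7 agrees. When its columns are aligned on rows whose visit is known (dispensing the activity tracker, insemination), the urine test is marked at screening, the monthly visits, the end of Phase 1, the Cycle 1 baseline and at home. The Baseline/Drug Assign cell is empty. The next scheduled test after screening is at the first monthly visit.

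Section 4.1.2 describes the women as actively seeking pregnancy, and nothing asks couples to stop trying between screening and randomization. On pregnancies in Phase I, Section 6.1.1 says "Of course such pregnancies will be analyzed by treatment group according to intention-to-treat (ITT) principles". Section 10.9 analyses all randomized women as assigned. Sections 1.6 and 10.3.1 define a cumulative outcome with no rule on the date of conception.

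**The concern.** An eligibility criterion needs to hold when the assignment is made. Here a negative result from eight weeks earlier satisfies every written testing requirement, in a population where pregnancy is the intended event. Because any cycle day is allowed, a recent period is not required either.

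Three things follow.

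- **Primary outcome.** A conception before randomization cannot be an effect of either intervention, yet a resulting good birth counts as a success for the assigned arm.
- **Time to pregnancy.** If the clock starts at randomization (Section 10.9 states no origin), some events will have conception dates before time zero.
- **Dispensing.** Section 6.1 hands intensive-arm women a two-month supply of orlistat at the randomization visit, while Section 6.1.1 has it discontinued immediately if pregnancy occurs. The visit schedule does not look for a pregnancy that is already present. These passages must be reconciled.

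**Working it through.** **1. The plan's own figure.** Section 10.4.1 states "A sample size of 190 per treatment arm will provide 80% power to detect a 0.15 absolute difference", "using a two-sided test having a significance level of 0.05". The rates are "We anticipate the proportion of good birth outcomes to be 0.25 in the standard lifestyle intervention" and "0.40 in the Intensive lifestyle modification arm". Two proportions, pooled variance, no continuity correction: 152 per arm, and 152/(1 − 0.20) = 190. This matches Table 11. Power at 152 per arm is 80.0%. The sample size itself is not in dispute.

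**2. A conception rate (assumption).** The documents give none. Section 10.4.1 says rates should exceed the preliminary data because of the extra 16 weeks of trying. Suppose the whole step from the obese clomiphene group in Table 6 (12/70 = 17.1%) to 0.25 comes from those weeks:

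- g = 1 − (1 − 0.25)/(1 − 12/70) = 0.0948 over 16 weeks
- weekly rate = −ln(1 − 0.0948)/16 = 0.0062, about 0.6% per week

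**3. Effect on the contrast.** Let q be the share of randomized women already carrying a pregnancy that will end in a good birth, equal in both arms by randomization. Each arm's rate becomes q + (1 − q)p, so the difference is 0.15(1 − q). For a window of d days, q = 1 − exp(−0.0062 × d/7). Power is at 152 per arm.

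| Window of conceptions | q | Women of 380 | Rates | Difference | Power |
|---|---|---|---|---|---|
| none | 0 | 0 | 0.250 v 0.400 | 0.150 | 80.0% |
| 7 days | 0.62% | 2.4 | 0.255 v 0.404 | 0.149 | 79.3% |
| 14 days | 1.24% | 4.7 | 0.259 v 0.407 | 0.148 | 78.5% |
| 30 days | 2.6% | 10.0 | 0.270 v 0.416 | 0.146 | 76.8% |
| 60 days | 5.2% | 19.7 | 0.289 v 0.431 | 0.142 | 73.6% |

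**4. Which row is plausible.** Assume, since the documents are silent, that a urine test becomes positive about 14 days after conception and that most women recognise a pregnancy by day 21 to 28. A test at randomization then catches 7 to 14 days' worth of conceptions, about 2 to 5 women. Conceptions in the last 14 days, about 5 more women, would still be missed. The 60-day row requires every screening test to be at its limit and no pregnancy to be recognised.

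**5. Uncertainty in the rate.** The exact 95% interval for 12/70 is 9.2% to 28.0%. At 9.2%, g = 1 − 0.75/0.908 = 0.174, the weekly rate is 1.2%, and the 7- and 14-day windows hold about 5 and 9 women (the 60-day window about 37). At 28.0% the preliminary rate already exceeds 0.25 and the implied rate is zero.

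**The case against.** The strongest reply is that the gap is narrow. Known or suspected pregnancy is already barred by Sections 5.2 and 5.6. These women ovulate regularly and are watching for pregnancy, so most conceptions 30 to 60 days old would be noticed. Section 7.2 allows randomization as soon as eligibility is met and expects that screening could be a single visit, so gaps may be short. Sites may also test on their own initiative. All of this stands. It limits the problem to unrecognised early pregnancy, but it does not supply the missing requirement.

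The conception rate is also open to challenge. Section 10.4.1 draws on two earlier trials and gives no split between natural conception and treatment. Section 3.4 suggests that exercise alone may favour reproduction, so part of the step to 0.25 may come from the standard arm's own intervention. That stands too, and it is why the rate is labelled an assumption.

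A reader might infer three stronger things that the documents do not support.

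- **That 10 to 20 contaminating births should be expected.** This treats long gaps as typical and ignores recognition.
- **That the comparison is biased in favour of one arm.** The conceptions precede assignment, so they are balanced in expectation.
- **That orlistat in early pregnancy is a new kind of exposure created by this gap.** Section 6.1.1 already welcomes conception during Phase I and tests are monthly, so exposure before detection is accepted for those pregnancies. What differs here is that the woman was ineligible when the drug was dispensed.

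**Conclusion.** The point holds as a verification gap. Followed as written, the plan can randomize women who meet an exclusion criterion and count births that neither arm could have caused. The statistical cost is dilution toward no difference and a small loss of power, and type I error is not inflated.

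If about 0.6% of women per week conceive a pregnancy ending in a good birth, and most pregnancies are recognised within 3 to 4 weeks, the number a test would remove is about 2 to 5 of 380. The upper end of that range costs 0.2 points of the assumed difference and 1.5 points of power. At the same rate, 20 women, 14.2 points and about 74% power form an upper bound for conceptions after the screening test. The rate and the recognition time are both assumptions.

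This does not invalidate the trial. It should still be corrected, because an existing exclusion can be made enforceable at almost no cost.

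**What to change.** - **Section 7.2, Randomization Visit, and Table 7, Baseline column:** add the urine pregnancy test and require a negative result before the assignment is requested.
- **Table 8 notes:** exempt this test from the 60-day window.
- **Section 10.9:** keep the intention-to-treat analysis of all randomized women as primary. Add a supportive sensitivity analysis that leaves out women whose conception, dated by scan or last menstrual period, precedes randomization. State its limits: conception can be dated only in pregnancies detected after open-label randomization, early losses may go undetected unequally by arm, and dating is imprecise close to the cut-off. It should not be presented as preserving the randomized comparison exactly.

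The cost is one test strip per woman at a visit that already takes place, a few more screen failures, and one extra analysis. Very recent conceptions will still be missed by the test.

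Separately, the sections on dispensing orlistat at randomization and on stopping it in pregnancy need to be reconciled with the visit schedule.

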This baseline visit will be performed at the start of Cycle 1 only. The initial dose of clomiphene citrate will be 100 mg/day, which may be adjusted upwards or downward depending on response in subsequent cycles. Women may undergo a total of up to 3 cycles culminating in hCG administration. Subjects may begin subsequent cycles immediately following failed cycles, as long as they meet baseline criteria of a negative urine pregnancy test. Subjects may continue in the study after one failed cycle (i.e. either no development of follicles on study medication). If a subject experiences a second failed cycle, it is recommended to discontinue the subject from the study.

1. Subject will call with menses and come in between days 1-5 of their menstrual cycle (Preferably day 3 for baseline monitoring visit).
2. Check Urine Pregnancy test.
3. Obtain weight.
4. Perform baseline ultrasound. If subject has a cyst with a mean diameter of >30mm, do not continue the visit. Have the subject return with her next menses for a repeat baseline visit.
5. Collect vaginal microbiome and rectal microbiome swab.
6. Dispense Infertility Treatment Study Medication (see Table 9). Please note, if the female has a prior history of over-response to clomiphene citrate at the 100mg dose, the starting dose may be adjusted downward.
7. Obtain central core lab specimens and blood and urine reserve (to be stored on site) for ancillary studies (with consent).

8. Dispense menstrual and intercourse diaries.
9. Schedule Day 8-12 visit for follicular monitoring.

Table 9: Study Medication and Dosing

Protocol	interval	dose	method	start	finish	future cycles
CC	Daily	100 mg	pill	Day 3*	Day 7	Can be started at 50-150 mg/d= (1 to 3 pills)

*(+/- 2 days)

Empirical treatment Cycle Visit number 2:

Within 3 days after completing 5-day drug cycle (Cycle Day 8-12)

1. Transvaginal ultrasound for endometrial and follicular monitoring.
2. Adverse effects and concomitant medications query.
3. During cycle 2 & 3, medication bottles and menstrual diaries from previous cycle will be collected.

Study treatment Cycle visits number 3 and beyond:

Visits for subjects will be conducted on an individualized basis until hCG administration. When a decision has been made to give hCG on the next day, a follow up monitoring visit on that day is unnecessary.

1. Transvaginal ultrasound examination for endometrial and follicular monitoring.
2. Adverse effects and concomitant medications query.

hCG administration day:

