1. 10,000 IU in 1 cc diluent delivered IM in clinic if applicable, or subjects will be instructed in the use of intramuscular hCG and a written plan for its use will be provided.
2. Transvaginal ultrasound examination for endometrial and follicular monitoring is not necessary if one has been performed within 2 days.

Criteria for hCG administration:

1. First occurrence of lead follicle reaching 20 mm (in average diameter in two dimensions), or
2. First occurrence of two lead follicles greater than 18 mm diameter (in average diameter in two dimensions), or
3. The day after the lead follicle reaching 18 mm (in average diameter in two dimensions), or
4. The day of detection of presumptive ovulation by ultrasound.

Criteria for withholding hCG:

1. If a leading follicle does not reach a mean diameter of 18 mm after 18 days of treatment, or

2. Endogenous LH surge happens [which can lead to premature luteinization], or
3. Increased risk for OHSS and/or high-order multiple gestational pregnancy exists when more than 4 growing follicles develop (mean diameter >18 mm)

**Protocol medication adjustment:*

1. If no ovulation or development of at least one follicle ≥ 18 mm in average diameter on treatment day 18, then bring subject in for a progesterone level and serum hCG. If the progesterone is less than 2.5 ng/ml and the hCG is negative, medication will be increased in a stair-step fashion to the maximum dose of 150mg. Progestin will not be used.
2. If only one follicle ≥ 18 mm in average diameter, the dosage increase for subsequent cycles will be left to physician's discretion.
3. If more than four follicles are ≥ 18 mm in average diameter, dosage will be reduced in the subsequent cycle. Dosage may also be reduced in a subsequent cycle if excessive follicular recruitment leads to cycle cancellation before follicles reach maturity
4. If the subject has an adverse reaction to the medication, the medication may be withheld for the remaining cycles.

**Cancellation criteria:* Cycles will be cancelled if significant adverse reactions develop in response to administered medications, if criteria for withholding hCG administration are encountered, or per patient's request.

Insemination protocol:

One insemination will be performed within 44 hours after hCG administration, and time of insemination from hCG administration will be recorded. For inseminations, each site will utilize its standard semen preparation method and catheter.

Insemination day visit:

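### Section 7.2 counts over-response with two cut-offs, more than four follicles >18 mm to withhold hCG but ≥18 mm to lower the next dose, so a woman over the dose limit may still receive hCG

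*Combined protocol and SAP*

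**What the plan says.** All the rules sit in section 7.2, in the description of the Phase 2 treatment cycle.

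- **When to give hCG.** Any one of four triggers is enough: a lead follicle of 20 mm; "First occurrence of two lead follicles greater than 18 mm diameter"; "The day after the lead follicle reaching 18 mm"; or presumptive ovulation on ultrasound.
- **When to withhold hCG.** There are three items: no lead follicle of 18 mm after 18 days, an endogenous LH surge, and over-response. The over-response item reads: "Increased risk for OHSS and/or high-order multiple gestational pregnancy exists when more than 4 growing follicles develop (mean diameter >18 mm".
- **When to cancel.** The grounds are a significant adverse reaction, the patient's request, and "if criteria for withholding hCG administration are encountered".
- **How to change the next dose.** Item 3 of the medication adjustment is mandatory in its first sentence: "If more than four follicles are ≥ 18 mm in average diameter, dosage will be reduced in the subsequent cycle". Its second sentence is permissive: "Dosage may also be reduced in a subsequent cycle if excessive follicular recruitment leads to cycle cancellation before follicles reach maturity".

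Section 9.2 adds no follicle criterion. It refers back to these visit descriptions.

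**The concern.** The withholding list is the protocol's stated check against OHSS and high-order multiple pregnancy before hCG is given, and section 8.1.2 names multiple pregnancy as a risk of clomiphene and hCG. The dose rule treats more than four follicles of 18 mm or larger as a response too strong to repeat at the same dose. The withholding rule uses the same count but leaves out follicles of exactly 18 mm. A site that follows both rules to the letter can therefore classify a response as excessive for the next cycle and still trigger ovulation in the present one.

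A smaller inconsistency lies beside it. The dose rule speaks of cycles cancelled for over-recruitment before maturity, but neither the withholding list nor the cancellation list gives that ground.

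**Working it through.** There is no stated figure to reproduce. The check applies the rules of section 7.2 to example scans.

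**General condition.** Let a be the number of follicles above 18 mm and b the number measured at exactly 18 mm.

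- Withhold and cancel: a > 4, that is a ≥ 5.
- Reduce the next dose: a + b > 4, that is a + b ≥ 5.
- The rules part when a ≤ 4 and a + b ≥ 5, so b ≥ 5 − a ≥ 1. One follicle at 18 mm is enough if four others are larger.

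In every such case the lead follicle is at least 18 mm. Trigger 3 is therefore met for the following day at the latest, and trigger 2 is also met when a ≥ 2. Withholding item 1 cannot apply, because the lead has reached 18 mm. Only an LH surge, which is a separate matter, would stop hCG.

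**Examples.**

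| Follicles (mm) | Triggers 1–3 met | Count >18 mm | hCG withheld? | Count ≥18 mm | Next dose reduced? |
|---|---|---|---|---|---|
| 20, 19, 19, 18, 18 | 1, 2, 3 | 3 | no | 5 | yes |
| 19, 19, 19, 19, 18 | 2, 3 | 4 | no | 5 | yes |
| 18.5, 18, 18, 18, 18 | 3 | 1 | no | 5 | yes |
| 18, 18, 18, 18, 18 | 3 | 0 | no | 5 | yes |
| 18.5 (five follicles) | 2, 3 | 5 | yes | 5 | yes |

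The first four scans fall in the gap. The last shows the two rules agreeing once all five follicles exceed 18 mm. With ≥18 mm in the withholding item, its count becomes a + b and all five rows give the same answer under both rules.

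**Early over-recruitment.** Of the three withholding items, one concerns under-response, one an LH surge, and one follicles already above 18 mm. The three cancellation grounds are an adverse reaction, any withholding item, and patient request. So 0 of 3 and 0 of 3 name over-recruitment before maturity, the event that the second sentence of dose item 3 presupposes.

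**The case against.** The strongest reply is that the two cut-offs govern different actions, this cycle's hCG and the next cycle's dose, and that a slightly lower bar for reducing a dose is not a contradiction. The mismatch also bites only at a measurement of exactly 18 mm. At any scan with more than four follicles above 18 mm the safeguard works as intended. Monitoring is flexible: "Visits for subjects will be conducted on an individualized basis until hCG administration". This largely stands and is why the point is minor. It does not remove the gap, because the protocol gives no reason for the two signs, and the looser one is attached to the more immediate risk.

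A second reply is that sites may have fuller instructions. Phase II is adapted from AMIGOS (section 6.1), and section 6.2 refers to a Manual of Operations and Procedures that is not available here. That limits what can be inferred about practice, but it does not mend the protocol text.

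A reader might draw stronger conclusions that the documents do not support:

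- **That hCG is allowed in cycles which the dose rule says should be cancelled.** The second sentence of dose item 3 is permissive and conditional. It sets the dose after a cancellation and does not say which cycles to cancel. It also concerns follicles that are not yet mature, when hCG is not normally due under triggers 1 to 3.
- **That many mid-size follicles beside a mature lead should block hCG** (for example one of 18.5 mm and five of 17.5 mm). No rule in the protocol addresses that scan. A cut-off below 18 mm would be a clinical preference.
- **That the last safety scan is forbidden.** The text says "When a decision has been made to give hCG on the next day, a follow up monitoring visit on that day is unnecessary". That makes a further visit unnecessary; it does not rule one out.

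**Conclusion.** The mismatch is real and rests on the wording alone. The over-response count is >18 mm where hCG is withheld and ≥18 mm where the dose must be reduced. A count that passes four only by including follicles of 18 mm makes the woman an over-responder under one rule and eligible for hCG under the other. The example of 20, 19, 19, 18 and 18 mm gives 5 against 3.

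The conclusion assumes that the signs are meant literally. The frequency of such scans cannot be estimated from the documents. The missing cancellation ground for early over-recruitment is a consistency point only.

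This is a minor participant-safety correction, worth making because it is cheap. Phase II is the same in both arms, so a reader should not infer bias, a loss of power or any effect on the comparison between arms.

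**What to change.** 1. In section 7.2, reword item 3 of the criteria for withholding hCG to: more than 4 follicles with mean diameter ≥18 mm. It then matches the dose rule, and cancellation follows without further change.
2. As a minor consistency edit, add one ground to the cancellation criteria: too many follicles recruited before maturity, at the investigator's judgement. Set no numeric cut-off below 18 mm.

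The cost is protocol wording, with no extra scan. The downside is a few more cancelled cycles, number unknown. A cancelled cycle does not use up one of the three cycles that end in hCG, but it takes time from the roughly 16 weeks that section 7.2 allows for Phase 2.
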